2.2 Handling Missing Data

All participants who were randomized on the parent protocol BMT CTN 0702 will be included in the analysis for BMT CTN 07LT. Data for patients not enrolled on the long-term follow-up protocol will be included with two parts combined: 1) 0702 data until their end of participation on the BMT CTN 0702 protocol; 2) follow up data provided through the Center for International Blood and Marrow Transplant Research (CIBMTR).

For time-to-event variables, participants who have not had an event or competing risk event will be censored at the time data for the endpoint is no longer available. For Quality of Life analyses, participants will be excluded at a particular time point if they do not complete the surveys within a +/- 90-day window for the particular time point in the analysis.

The time of progression that was adjudicated on BMT CTN 0702 by the 0702 Endpoint Review Committee (ERC) will be used for participants who progressed on BMT CTN 0702. There is no adjudication of progression on BMT CTN 07LT, so progression will be determined by site-reported responses.

For the primary endpoint of PFS and the secondary endpoints of EFS, overall survival and cumulative incidence of SPM, and for tabulation of cause of death, data from the BMT CTN 0702, BMT CTN 07LT, and from the CIBMTR will be used.

2.3 Multiple Comparisons

All tests for treatment group differences that compare 2 groups at a time will be compared at the 0.05/3 significance level to adjust for the pairwise testing. Kaplan Meier estimates, cumulative incidence estimates, and hazard ratios for treatment groups will be presented with 98.3% confidence limits.

2.4 Interim Analyses and Stopping Guidelines

There will be no interim analyses on BMT CTN 07LT and no adjustments for prior testing of the endpoints on the 0702 study.

There are no official stopping guidelines for BMT CTN 07LT. The BMT CTN DSMB monitors the safety and efficacy data on an approximate 6-month basis, and makes recommendations to the NHLBI regarding release of data to investigators and the general public.

2.5 Timing of Analysis

Follow-up for the BMT CNT 07LT protocol continues until the end of 2018; this is approximately when all living patients have been enrolled for 5-years post randomization on the BMT CTN 0702 protocol. The BMT CTN 07LT analysis will begin upon the completion of all data entry and cleaning including retrieval of CIBMTR data after the follow-up is finished.

2.6 Software

All analyses will be conducted using SAS version 9.4 or higher, or R version 3.3.2 or higher.

2.7 Analysis Populations

The following analysis populations will be used:

0702-enrolled	Will include all patients randomized on protocol BMT CTN 0702. Data from the BMT CTN 0702 protocol, BMT CTN 07LT protocol, and CIBMTR will be used
07LT-enrolled	Will include patients enrolled on protocol BMT CTN 07LT only. Data will be limited to data provided during 07LT follow-up. This population will be used for tabulation of unexpected grades 3-5 events, analysis of health quality of life, and study protocol deviations.

Some of the analyses will use a subset of these populations. These are described in the section for each endpoint.

2.7.1 Primary Analysis Population

0702-enrolled population

The primary analysis population, 0702-enrolled population, will include all participants randomized on the parent trial, BMT CTN 0702, in the arm to which they were assigned (intent-to-treat), regardless of treatment received. This population will be used for the analysis of the primary endpoint, PFS, as well as for the secondary endpoints of overall survival, EFS, and SPM. This population will be used to tabulate reasons for permanent withdrawal from lenlidomide maintenance therapy.

07LT-enrolled population

The 07LT-enrolled population will include all participants enrolled on BMT CTN 07LT. This population will be used for the analysis of adverse events and of health quality of life, and for descriptions of study accrual, and study protocol deviations.

No adjustments for post-randomization review of eligibility.

For analyses with the 0702-enrolled population, all participants for the BMT CTN 0702 trial will be included in the BMT CTN 07LT analysis, even those adjudicated to be ineligible by the BMT CTN 0702 Endpoint Review Committee or determined to be ineligible after data review post enrollment. Similarly, analyses limited to the 07LT population will include all participants enrolled on BMT CTN 07LT, including any participants determined post enrollment to be ineligible for BMT CTN 07LT.

2.7.2 Safety Analysis and Analysis Population

The 07LT-enrolled population is comprised of two groups of participants – those who are taking long-term lenalidomide maintenance therapy, and those who have never started maintenance therapy. Safety data is collected differently for participants taking lenalidomide and or patients who never stated lenalidomide on 07LT or discontinued it.

For participants enrolled on BMT CTN 07LT who are taking long-term lenalidomide maintenance therapy, unexpected, grades 3-5 adverse events will be reported through the expedited AE reporting system in AdvantageEDC using NCI's Common Terminology Criteria for Adverse Events (CTCAE) Version 4.0. Unexpected, grade 4-5 AEs must be reported within 24 hours of knowledge of the event. Unexpected, grade 3 AEs must be reported within three business days of knowledge of the event. Selected expected serious AEs (protocol Appendix F - Table F-1) require expedited reporting. Additionally, selected AEs of interest (protocol Appendix F - Table F-2) will require expedited reporting, if they fulfill serious criteria according to the Code of Federal Regulations Title 21 (21 CFR 312.32) and occur after the administration of lenalidomide and up to 30 days after the permanent discontinuation of lenalidomide. See protocol Appendix F for additional details on expedited reporting.

For participants enrolled on BMT CTN 07LT follow-up only, or for BMT CTN 07LT participants who have permanently discontinued lenalidomide maintenance for more than 28-30 days, or for participants who have met the protocol defined definition of progression, reporting of

unexpected grades 3-5 adverse events, selected serious AEs, or selected AEs of interest will not require reporting with the exception of second primary malignancies.

Deaths are required to be reported for all patients enrolled on 07LT within 24 hours of the site's knowledge of the patient's death.

Unexpected grades 3-5 adverse events will be tabulated and compared across treatment arms for the BMT CTN 07LT population. Summaries by type and severity of adverse events will be provided. Safety data will be summarized using Medical Dictionary for Regulatory Activities (MedDRA) Coding Version 20.0 or above.

Secondary primary malignancies (SPMs) in the BMT CTN 0702 population will be analyzed as a secondary outcome using cumulative incidence curves and Gray's test for treatment group comparisons. SPMs will also be described by treatment group and histologic type.

Primary causes of deaths will be tabulated, and survival will be analyzed as a secondary outcome using Kaplan Meier curves and stratified log rank tests.

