## 2.5. Supportive Care

### 2.5.1. Deep Vein Thrombosis (DVT) and Pulmonary Embolism (PE) Prophylaxis

Patients receiving dexamethasone and thalidomide as remission induction therapy for MM have an increased risk of developing DVT/PE. This risk may be as high as 10%. It is unclear whether the risk is the same in patients receiving lenalidomide as a single agent and as maintenance therapy after autologous transplantation. Treating physicians should be aware of this risk and have heightened vigilance regarding this possible toxicity. Aspirin should be administered per institutional guidelines during lenalidomide maintenance therapy unless the patient is treated with alternate prophylaxis of either low molecular weight heparin or coumadin.

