**TABLE F-1: SERIOUS ADVERSE EVENTS THAT REQUIRE EXPEDITED REPORTING BY INDIVIDUAL CASE SAFETY REPORTS (ICSR)**

Adverse Event	Seriousness or Capture Method	Collection Form
ALLERGY/IMMUNOLOGY		
Anaphylactic reaction	SAE	ICSR
CARDIAC		
Asystole	SAE	ICSR
Atrial Ventricular Block	SAE	ICSR
Congestive Heart Failure	SAE	ICSR
Myocardial Infarction	SAE	ICSR
Pericarditis	SAE	ICSR
Pericardial disease	SAE	ICSR
Pericardial effusion (including tamponade)	SAE	ICSR
Prolongation of QTc interval	SAE	ICSR
Sinus Bradycardia	SAE	ICSR
Supraventricular Tachycardia	SAE	ICSR
Ventricular Tachycardia	SAE	ICSR
Pulmonary hypertension	SAE	ICSR
COAGULATION		
Disseminate intravascular coagulation (DIC)	SAE	ICSR
DERMATOLOGY		
Erythema multiforme (toxic epidermal necrolysis)	SAE	ICSR
Sweet's Syndrome (acute neutrophilic dermatosis)	SAE	ICSR

Adverse Event	Seriousness or Capture Method	Collection Form
Pyoderma gangrenosum	SAE	ICSR
Vasculitis	SAE	ICSR
ENDOCRINE		
Hyperthyroidism	SAE	ICSR
GASTROINTESTINAL		
Ileus (functional obstruction of bowel, i.e., neuroconstipation)	SAE	ICSR
GI Perforation	SAE	ICSR
Diverticulitis	SAE	ICSR
Ischemic bowel	SAE	ICSR
HEMORRHAGE		
Central Nervous system	SAE	ICSR
HEPATOBIILIARY/PANCREAS		
Liver dysfunction/failure (Clinical - CTCAE)	SAE	ICSR
Pancreatitis	SAE	ICSR
NEUROLOGY		
Neurology – Peripheral neuropathy	SAE	ICSR
Neuropathy: Motor	SAE	ICSR
Neuropathy: Sensory	SAE	ICSR
Syncope (fainting) 	SAE	ICSR
CNS ischemia	SAE	ICSR
Coma	SAE	ICSR
Cranial palsy	SAE	ICSR
Seizure	SAE	ICSR
Spinal cord compression	SAE	ICSR
Brain Edema	SAE	ICSR
Encephalopathy	SAE	ICSR
Leukoencephalopathy syndrome including reversible posterior leukoencephalopathy syndrome [RPLS]) or (Leukoencephalopathy radiographic findings)	SAE	ICSR
PULMONARY/UPPER RESPIRATORY		
Acute Respiratory Distress Syndrome	SAE	ICSR
Alveolar Hemorrhage	SAE	ICSR
Pleural effusion (non-malignant)	SAE	ICSR
Pneumonitis/Pulmonary Infiltrates (absence of infection)	SAE	ICSR
Pulmonary Hypertension	SAE	ICSR

Adverse Event	Seriousness or Capture Method 	Collection Form
RENAL/GENITOURINARY		
Renal failure	SAE	ICSR
SYNDROMES		
Tumor flare	SAE	ICSR
Tumor lysis syndrome	SAE	ICSR
VASCULAR		
Acute vascular leak syndrome	SAE	ICSR
DEATH		
Sudden death	SAE	ICSR
OTHER		
Second malignancies	SAE	ICSR

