 Serious Adverse events are defined by the 21 CFR (312.32a): AE that results in death, requires hospitalization, persistent or significant disability or incapacity, congenital anomaly, that is life threatening or considered as medically important.

**TABLE F-2: EXPECTED ADVERSE EVENTS OF INTEREST THAT WILL REQUIRE EXPEDITED REPORTING IF THEY MEET SERIOUS ADVERSE EVENT CRITERIA AND OCCUR AFTER THE INITIATION OF LENALIDOMIDE AND THROUGH 28 DAYS AFTER THE DISCONTINUATION OF LENALIDOMIDE**

Adverse Event	Seriousness or Capture Method 	Collection Form
AUDITORY/EAR		
Hearing loss	SAE	ICSR
CARDIAC		
Atrial fibrillation	SAE	ICSR
Atrial flutter	SAE	ICSR
COAGULATION		
Deep vein thrombosis	SAE	ICSR
Pulmonary emboli 	SAE	ICSR
HEMORRHAGE		
Hemorrhage, Gastrointestinal	SAE	ICSR
Hemorrhage, Pulmonary	SAE	ICSR
METABOLIC/LABORATORY		
Elevation of ALT $\geq 2.5x$ ULN	SAE	ICSR
Elevation of AST $\geq 2.5x$ ULN	SAE	ICSR
Elevation of Bilirubin $\geq 3x$ ULN	SAE	ICSR
MUSCULOSCELETAL/SOFT TISSUE		
Muscular weakness	SAE	ICSR
NEUROLOGY		
Neurology – Peripheral neuropathy	SAE	ICSR

Adverse Event	Seriousness or Capture Method	Collection Form
Neuropathy: Motor	SAE	ICSR
Neuropathy: Sensory	SAE	ICSR
Syncope (fainting)	SAE	ICSR
OCULAR/VISUAL		
Vision – Blurred vision	SAE	ICSR
PAIN		
Pain – Neuralgia	SAE	ICSR
INFECTION		
Febrile neutropenia	SAE	ICSR
DEATH		
Sudden death	SAE	ICSR
OTHER		
Second malignancies	SAE	ICSR

 Serious Adverse events as defined by the 21 CFR (312.32a): AE that results in death, requires hospitalization, persistent or significant disability or incapacity, congenital anomaly, that is life threatening or considered as medically important.

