			F	First Event ³			
Comparison	N	Total Number with an Event	PRG or NPT	SPM	ртн	p-value ¹	
Auto/Auto to	247	XXX	XXX	XXX	XXX	0.XX	
Auto/RVD	254	XXX	XXX	XXX	XXX		
Auto/Auto to	247	XXX	XXX	XXX	XXX	0.XX	
Auto/Maintenance	257	XXX	XXX	XXX	XXX		
Auto/RVD to	254	XXX	XXX	XXX	XXX	0.XX	
Auto/Maintenance	257	XXX	XXX	XXX	XXX		

¹Significance level is 0.05/3 for each pairwise comparison.

Exhibit 07LT-7: Cumulative Incidence of First SPM

Figure template for illustration only

Cumulative Incidence of First SPM by Treatment Arm

Cumulative Incidence Estimates and 98.3% Confidence Intervals

	Auto/Auto	Auto/RVD	Auto/Maint		
5-year Estimates:	XX.X (XX.X, XX.X)	XX.X (XX.X, XX.X)	XX.X (XX.X, XX.X)		

Stratified Gray's Test for Treatment Group Differences

Treatment Group Comparison	p-value ¹
Auto/Auto vs Auto/RVD	0.XX
Auto/Auto vs Auto/Maint	0.XX
Auto/RVD vs Auto/Maint	0.XX

¹Significance level is 0.05/3 for each pairwise comparison.

Exhibit 07LT-8: SPM Histologic Type

	Au	Auto/Auto		Auto/RVD		Auto/Maint		Total
	N	%	N	%	N	%	N	%
All ¹	XXX	100.0	XXX	100.0	XXX	100.0	XXX	100.0
Hematologic SPM	XXX	XX.X	XXX	XX.X	XXX	XX.X	XXX	XX.X
High-Level Group Term 1	XXX		XXX		XXX		XXX	
High-Level Group Term 2	XXX		XXX		XXX		XXX	
(etc.)	XXX		XXX		XXX		XXX	
Solid Tumor SPM	XXX	XX.X	XXX	XX.X	XXX	XX.X	XXX	XX.X
High-Level Group Term 1	XXX		XXX		XXX		XXX	
High-Level Group Term 2	XXX		XXX		XXX		XXX	
(etc.)	XXX		XXX		XXX		XXX	

¹More than one SPM may be reported per participant. SPM reporting on BMT CTN 0702 and 07LT is not required after progression. Supplemental data is provided by the CIBMTR.

Exhibit 07LT-9A: Unexpected Grades 3-5 Adverse Events in Participants Initiating Lenalidomide on BMT CTN 07LT¹

		Auto/Auto	Auto/RVD	Auto/Maint	
		N %	N %	N %	Total
All Unexpected Grades 3-5 Adverse Events		XX 100.0	XX 100.0	XX 100.0	XX 100.0
System Organ Class	Preferred				
(SOC)	Term				
SOC1	ALL	XX XX.X	XX XX.X	XX XX.X	XX XX.X
	PT1	(just N)	(just N)	(just N)	(just N)
	PT2	(just N)	(just N)	(just N)	(just N)
SOC2	ALL	XX XX.X	XX XX.X	XX XX.X	XX XX.X
	PT1	(just N)	(just N)	(just N)	(just N)
	PT2	(just N)	(just N)	(just N)	(just N)
(etc.)	(etc.)				
Severity					
Grade 3		XX XX.X	XX XX.X	XX XX.X	XX XX.X
Grade 4		XX XX.X	XX XX.X	XX XX.X	XX XX.X
Grade 5		XX XX.X	XX XX.X	XX XX.X	XX XX.X

¹ The reporting requirements differ for participants taking lenalidomide.

Exhibit 07LT-9B: Unexpected Grades 3-5 Adverse Events in Participants Enrolled on BMT CTN 07LT Who Did Not Initiate Lenalidomide

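### Serious expected events on 07LT lenalidomide (Tables F-1 and F-2) are collected by expedited report, but the SAP specifies no adverse event table for them

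*SAP*

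**What the plan says.** **Collection.** Protocol 4.3.1 and Appendix F require individual case safety reports for participants on long-term lenalidomide, beyond those for unexpected grades 3-5 events. SAP 2.7.2 repeats this for Table F-1, "Selected expected serious AEs (protocol Appendix F - Table F-1) require expedited reporting", and for Table F-2, "Additionally, selected AEs of interest (protocol Appendix F - Table F-2) will require expedited reporting, if they fulfill serious criteria". Appendix F introduces the Table F-1 events as expected, and the title of Table F-2 reads "EXPECTED ADVERSE EVENTS OF INTEREST THAT WILL REQUIRE EXPEDITED REPORTING".

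**Analysis.** SAP 2.7.2 then states the tabulation: "Unexpected grades 3-5 adverse events will be tabulated and compared across treatment arms for the BMT CTN 07LT population". SAP 2.7 (population table) and SAP 4.2 carry the same restriction, as do protocol 3.3.4 and 5.4. The shell for lenalidomide recipients, Exhibit 07LT-9A, is titled "Unexpected Grades 3-5 Adverse Events in Participants Initiating Lenalidomide on BMT CTN 07LT". Exhibit 9B is its counterpart for participants who did not start the drug on 07LT.

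**Other safety outputs.** The SAP plans cumulative incidence and histology of SPMs (Exhibits 7 and 8), overall survival (Exhibit 5), reasons for permanent discontinuation of lenalidomide (Supplemental Exhibit 3) and primary cause of death (Supplemental Exhibit 4).

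**The concern.** Events classed as expected are, by that label, the serious harms already anticipated with the drug. Protocol 2.6.1 lists thromboembolism, neutropenia, liver damage and renal failure among lenalidomide toxicities. Protocol 2.3.3 bars patients from long-term maintenance after a thromboembolic event on full anticoagulation, or if they refuse DVT prophylaxis. On DVT and pulmonary embolism, protocol 2.5.1 says: "It is unclear whether the risk is the same in patients receiving lenalidomide as a single agent". The study collects reports that bear on that question, in patients treated beyond three years, and specifies no summary of them. A reader of Exhibit 9A would see the unanticipated events and not, as a rule, the anticipated ones.

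**Working it through.** The point depends on which events are collected and which are tabulated. The plan states no figure to reproduce.

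**1. Count the listed terms (protocol Appendix F).**
- Table F-1, rows by body system in the order printed: 1 + 12 + 1 + 4 + 1 + 4 + 1 + 2 + 12 + 5 + 1 + 2 + 1 + 1 + 1 = 49. Pulmonary hypertension appears twice (cardiac and pulmonary), so there are 49 − 1 = 48 distinct terms.
- Table F-2, rows in the order printed: 1 + 2 + 2 + 2 + 3 + 1 + 4 + 1 + 1 + 1 + 1 + 1 = 20.
- Six terms are in both tables: peripheral neuropathy, motor neuropathy, sensory neuropathy, syncope, sudden death and second malignancies.
- Distinct terms: 48 + 20 − 6 = 62.

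**2. Match the terms to the SAP exhibits.** Second malignancies reach Exhibits 7 and 8. Sudden death reaches overall survival and the cause-of-death table. That leaves 62 − 2 = 60 terms with no planned adverse event summary.

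**3. Place the clinically prominent examples.**

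| Event | Listed in | Planned adverse event table |
|---|---|---|
| Myocardial infarction | F-1 | none |
| Renal failure | F-1 | none |
| Liver dysfunction or failure | F-1 | none |
| Deep vein thrombosis | F-2 | none |
| Pulmonary embolism | F-2 | none |
| Febrile neutropenia | F-2 | none |

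**4. Ask whether another planned output would catch them.** Supplemental Exhibit 4 shows an event only if it was fatal. Where the endpoint committee has not adjudicated the cause, prior progression or an SPM takes precedence over the site-reported cause. Supplemental Exhibit 3 shows an event only if it led to permanent discontinuation, and perhaps then only under a broad reason. Protocol Table 2.4.2a provides for holding and restarting lenalidomide after grade 3 or higher venous thrombosis or embolism. Table 2.4.2c provides, at all but the lowest dose step, for a hold and a restart once counts recover. A non-fatal embolism or febrile neutropenia handled in that way need not appear in any planned output.

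**5. What cannot be computed.** The documents give no number of participants on 07LT lenalidomide and no rate for any listed event, so there is no basis for a count of untabulated events.

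**The case against.** The case on the other side has five parts.

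- **The SAP follows the protocol.** Protocol 3.3.4 and 5.4 define the adverse event endpoint as unexpected grades 3-5, the primary objective is PFS by randomized arm, and the exhibits are openly titled as unexpected events. This stands: the proposed table is an addition and corrects no departure from the protocol.
- **The wording is not wholly closed.** SAP 2.7.2 also promises summaries of adverse events by type and severity, SAP 2.7.1 assigns the 07LT population to adverse event analysis, and SAP Section 5 calls the shells illustrative. But the type-and-severity sentence directly follows the restricted one, and SAP 4.2 repeats that wording under the heading for unexpected events. No text or shell extends it to Tables F-1 and F-2.
- **The table could be added later.** SAP 2.8 allows ad hoc analyses, but they must be labelled as not pre-planned. That is a poor status for known serious harms.
- **The DSMB sees safety data about every six months.** That is oversight during the study. It does not fix the content of the final report.
- **Other safety outputs exist.** This stands and limits the point. A reader might infer that long-term lenalidomide is judged on unexpected events alone. The documents do not support that: SPMs are on both lists and are a secondary endpoint with their own tests, and deaths by cause and reasons for stopping are tabulated.

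Two further inferences also go too far. One is that Exhibit 9A must by construction contain no listed event. Neither document defines unexpected, and protocol 4.3.1 defers to a manual of procedures that is not among the documents, so a listed term might still qualify, for instance by its severity. The other is that listed events are reported within days. The 24-hour and three-business-day limits in protocol 4.3.1 are stated for unexpected events, and the only limit tied to a listed term is the three business days for SPMs in 4.3.2.

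**Conclusion.** The gap is real but bounded. Apart from SPMs, causes of death and reasons for permanent discontinuation, the only adverse event tables planned cover unexpected grades 3-5 events. Sixty of the 62 distinct terms in Tables F-1 and F-2 are collected by expedited report from participants on 07LT lenalidomide and have no planned adverse event summary. The final report is therefore likely to understate known serious toxicity in these participants. The conclusion rests on reading the type-and-severity sentence in its context and on the listed terms generally being handled as expected, which is how Appendix F describes them. It does not affect the PFS comparison, its alpha or any other efficacy analysis. The change should be made because the data are already required and the omission concerns the drug's anticipated serious harms.

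**What to change.** 1. In SAP 2.7.2 and 4.2, extend the tabulation sentences to cover serious events listed in protocol Tables F-1 and F-2 as well as unexpected grades 3-5 events. Align the population table in SAP 2.7 and record the addition in SAP 2.8.1.
2. Add a descriptive Exhibit 07LT-9C for participants who initiated lenalidomide on 07LT. Give the number and percent with at least one event, by MedDRA system organ class, preferred term and grade, by randomized arm and in total. Count a term listed in both tables once.
3. State on the exhibit that it cannot be compared with participants not on lenalidomide, because these reports are not required from them.
4. Reconcile the reporting window before the table uses one. The title of Table F-2 runs to 28 days after discontinuation, protocol 4.3.1 and SAP 2.7.2 give 30 days, and a later paragraph of SAP 2.7.2 gives 28-30 days.

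The cost is SAP wording and one extra table from reports the protocol already has sites submit on the Adverse Event Forms. No hypothesis, sample size or alpha changes. The reported safety profile may look less favourable.

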2.8 General Analysis Guidelines

There are no planned sub-group analyses or sensitivity analyses.

Any changes to the planned analyses or any ad hoc analyses will be documented and clarified in each analysis report (through the time of the report) and may be documented in updated versions of the SAP. Ad hoc analyses will be included as supplemental exhibits and noted to be analyses that are not part of the pre-planned analyses.

There are no pre-defined ancillary studies for the BMT CTN 07LT protocol. Optional research samples for future analysis are being collected for those enrolled in 07LT. Any analyses with these samples will be described separately and will be conducted at time points not affecting the analyses described in this SAP.

2.8.1 Changes to the planned analyses

Clarifications from the BMT CTN 07LT protocol

The protocol specified that for the primary endpoint of PFS, deaths will be counted as failures no matter when they occur. This is clarified to note that deaths that occur prior to the end of 2018 will be counted as failures and deaths that occur after progression will use time to progression rather than time to death for the primary analysis. Deaths through the end of follow-up in December 2018 will be counted, but deaths that occur between the end of BMT CTN 07LT in December 2018 and the database closure for the analysis will not be counted.

The protocol specified that for some of the secondary outcomes, the analysis would be completed once all alive patients have been followed for 5-years post randomization on the BMT CTN 0702 protocol. This is clarified to note that the secondary outcomes will be analyzed at the same time as the primary analysis -- once all alive patients have been followed for 5-years post randomization on the BMT CTN 0702 protocol or the end of 2018.

The protocol specified that a Cox model would be used to analyze PFS data, but did not require that treatment group and risk strata be included in the model. These factors will be included in the models.

Supplemental analyses of EFS and OS have been added to incorporate a Cox model analysis adjusting for baseline risk factors for the 0702-enrolled population and to incorporate a Cox model investigating EFS, baseline risk factors, and discontinuation of lenalidomide among the population that initiated maintenance therapy. Additional cause-specific analyses will show the Cox model results for each component of EFS, with censoring at the time of the other components.

Additional supplemental landmark analyses of PFS, OS, and EFS have been added to explore these outcomes between those on long term lenalidomide and those not on long term lenalidomide.

3. Participant Characteristics and Compliance

